4.2 Participants

Approximately 18 participants with anxiety or depressive distress will be recruited.

Inclusion Criteria

Age ≥ 18 years

Experience of emotional distress

Ability to understand and communicate in Chinese

Provision of informed consent

Exclusion Criteria

Acute psychosis or severe psychiatric disorders

Cognitive impairment

4.3 Procedure

Semi-structured interviews (~50 minutes) will include:

Rapport building

Cognitive interviewing (think-aloud + probing)

Structural evaluation

4.4 Data Analysis

Thematic analysis will be conducted:

Open coding

Theme development

Mapping to item pool

Two independent coders will analyze data.

5. Study 2: Quantitative Phase

5.1 Participants

Participants will be recruited using random sampling.

Sample size:

5–10 participants per item, 550.

5.2 Measures

Excessive Emotional Behaviors Scale (Preliminary Version)

Developed based on qualitative phase.

Experiential Avoidance Measures

Acceptance and Action Questionnaire–II

Brief Experiential Avoidance Questionnaire

Anxiety Measure

Generalized Anxiety Disorder Scale–7

Depression Measure

Patient Health Questionnaire–9

6. Statistical Analysis Plan

This study aims to develop the Excessive Emotional Behavior Scale to assess emotional behavior patterns exhibited by individuals experiencing emotional distress. Based on the theoretical framework, the initial item pool will consist of 40 items covering four hypothesized dimensions: behavioral avoidance, cognitive avoidance, safety behavior, and emotion-driven behavior. To ensure the stability of the scale structure and the psychometric quality of the instrument, a two-stage independent-sample design will be used for scale development and validation. In the first stage, an independent sample will be recruited for item analysis and exploratory factor analysis to establish the preliminary structure of the scale. In the second stage, a new independent sample will be recruited for confirmatory factor analysis, as well as reliability and validity testing, to determine the final item composition and dimensional structure of the formal scale.

6.1 Sample Use Strategy

A two-stage independent-sample design will be adopted in this study. In the first stage, one independent sample will be recruited for item analysis and exploratory factor analysis to preliminarily screen items and explore the latent factor structure of the scale. In the second stage, another new independent sample will be recruited for confirmatory factor analysis to test the stability and replicability of the factor structure identified in the first stage. This design helps avoid the risk of overfitting that may arise when structural exploration and structural validation are conducted within the same sample, thereby improving the rigor of structural validation and the

external stability of the findings.

The first-stage sample will be used only for item analysis and exploratory factor analysis and will not be used for confirmation of the final structural model. The second-stage sample will be used independently for confirmatory factor analysis, internal consistency testing, and the evaluation of structural validity, convergent validity, discriminant validity, and criterion-related validity. If the sample size in the second stage permits, additional competing model comparisons and supplementary model testing will also be conducted.

6.2 Data Preparation and Preprocessing

Before formal analyses, data cleaning and preprocessing will be conducted. This will include checking for missing values, abnormal response patterns, extreme values, duplicate responses, and unusually short completion times. Clearly invalid questionnaires, such as those showing large sections of invariant responses, extremely short response times, or obviously illogical response patterns, will be excluded according to pre-specified quality control criteria.

For missing data, the proportion of missing values for each item and the overall level of missingness will first be reported. If the proportion of missing data is low, appropriate imputation strategies or available-case methods may be used in specific analyses. If an estimation method suitable for handling missing data is used in the confirmatory factor analysis stage, that method will be preferred. All missing-data handling procedures will be explicitly reported in the results.

Descriptive statistics for each item, including mean, standard deviation, skewness, and kurtosis, will also be examined to assess item dispersion and distributional characteristics and to identify potential floor or ceiling effects. If an item shows an overly concentrated distribution, insufficient variance, or weak discriminatory power, its retention will be evaluated in combination with subsequent item analysis results.

6.3 Stage 1: Item Analysis and Exploratory Factor Analysis

6.3.1 Item Analysis

In the first stage, item analysis will first be conducted on the 40 initial items to evaluate item discrimination and the association of each item with the overall scale. The specific procedures are as follows.

First, participants will be divided into the upper 27% and lower 27% groups based on the total scale score. Independent-samples t-tests will then be used to compare item scores between the high-score and low-score groups, and the critical ratio for each item will be calculated. In general, if an item has a critical ratio below 3, or if the difference between the high-score and low-score groups does not reach statistical significance ($P \geq 0.05$), the item will be considered to have insufficient discrimination and may be considered for deletion.

Second, Pearson correlation coefficients between each item and the total scale score will be

calculated. Items with item-total correlations below 0.35 will be considered weakly associated with the overall construct and may be considered for removal. For items with very low or directionally abnormal correlations with the total score, further judgment will be made in light of item content and theoretical relevance.

In addition, item communalities will be examined. If an item has a communality below 0.20, this will suggest that the item is not well explained by the latent factor structure and may be considered a candidate for deletion. Item deletion at this stage will not be based on any single statistical criterion alone; rather, it will be determined by integrating item discrimination, item-total correlation, communality, content representativeness, and theoretical relevance.

6.3.2 Suitability Testing for Exploratory Factor Analysis

After item analysis is completed, exploratory factor analysis will be conducted on the retained items. Before factor extraction, the suitability of the sample for factor analysis will be assessed using the Kaiser-Meyer-Olkin (KMO) measure of sampling adequacy and Bartlett's test of sphericity. In general, a KMO value greater than 0.70 and a statistically significant Bartlett's test ($P < 0.001$) will be considered evidence that the data are suitable for factor analysis.

6.3.3 Factor Extraction Method and Rotation

Because the purpose of this study is to identify latent construct structure rather than simply reduce data, exploratory factor analysis will be conducted using principal axis factoring or maximum likelihood extraction. As behavioral avoidance, cognitive avoidance, safety behavior, and emotion-driven behavior are theoretically expected to be correlated, an oblique rotation method, such as Promax or Oblimin, will be used to better reflect the underlying psychological structure.

If the items are rated using Likert-type response options and the data characteristics are more consistent with ordinal categorical variables, factor extraction methods based on an appropriate correlation matrix for ordinal data will be preferred. If the data approximate continuous distributions and show satisfactory distributional properties, this will be noted and justified in the interpretation of the results.

6.3.4 Determination of the Number of Factors

The number of factors will be determined based on multiple sources of evidence rather than relying solely on the eigenvalue-greater-than-one rule. Specifically, the decision will be based on parallel analysis, the scree plot, eigenvalues, the theoretical interpretability of the factors, and the distribution of items across factors. Priority will be given to a factor solution that is consistent with the theoretical framework and has clear psychological meaning; however, if the empirical results deviate from the theoretical expectations, decisions will be made cautiously by integrating statistical evidence and theoretical reasoning.

6.3.5 Item Retention Criteria

The following criteria will be used for item retention during the exploratory factor analysis stage: the primary loading of an item on its intended factor should be at least 0.45; if an item has relatively high loadings on two or more factors, the difference between the primary loading and the secondary loading should be greater than 0.20 to avoid substantial cross-loading; items with very low communalities, unclear factor membership, or obvious content redundancy will also be considered for deletion. In addition to statistical criteria, the completeness of content coverage within each dimension will also be taken into account to avoid compromising construct representativeness in pursuit of statistical optimization alone.

A stepwise item reduction strategy will be used. After each deletion, exploratory factor analysis will be rerun until a candidate version of the scale with a clear structure, well-defined item-factor relationships, satisfactory statistical indicators, and sound theoretical interpretability is obtained. At the end of the first stage, a preliminary structural model and a candidate set of items for the Excessive Emotional Behavior Scale will be established.

6.4 Stage 2: Confirmatory Factor Analysis

6.4.1 Independent-Sample Validation Strategy

After completion of the first stage, a new independent sample will be recruited for confirmatory factor analysis. This sample will not be involved in item analysis or exploratory factor analysis, thereby ensuring that the exploration and validation processes remain independent. The primary purpose of the second stage is to test the stability of the scale structure identified in the first stage and to evaluate the fit of alternative structural models.

6.4.2 Model Specification

Confirmatory factor analysis will first be used to test the four-factor structure identified in the exploratory factor analysis. If theoretically warranted, several competing models may also be compared, such as a one-factor model, a correlated four-factor model, and a higher-order factor model, in order to evaluate the relative fit of the target model. All model comparisons will be guided by theoretical considerations rather than purely data-driven model building.

6.4.3 Estimation Method

If the items use Likert-type response options and are more appropriately treated as ordinal categorical variables, an estimation method suitable for ordinal data, such as WLSMV, will be preferred. If the item distributions approximate continuous variables and meet the relevant statistical assumptions, maximum likelihood estimation may also be used. The final estimation method will be determined based on the response format, distributional characteristics, and model convergence, and this choice will be clearly reported in the results.

6.4.4 Model Fit Evaluation Criteria

Model fit will be evaluated using multiple fit indices, including the chi-square to degrees of freedom ratio (χ^2/df), Comparative Fit Index (CFI), Tucker-Lewis Index (TLI), Root Mean Square Error of Approximation (RMSEA), and Standardized Root Mean Square Residual (SRMR). In general, CFI and TLI values greater than 0.90 will indicate acceptable model fit, and values greater than 0.95 will indicate good fit; RMSEA and SRMR values below 0.08 will indicate acceptable fit, and values below 0.06 will indicate good fit. Fit indices will be interpreted comprehensively rather than mechanically based on a single cutoff.

6.4.5 Principles for Model Modification

If the initial model does not achieve satisfactory fit, limited model modifications may be considered based on modification indices. However, all modifications must be supported by clear theoretical justification, such as residual correlations arising from semantically similar items or items whose content deviates from the intended dimension. Overfitting based solely on modification indices will be avoided in order to preserve the theoretical interpretability and structural stability of the model.

6.5 Stage 3: Reliability and Validity Testing

6.5.1 Internal Consistency Reliability

After the formal structure of the scale has been established in the second stage, internal consistency will be evaluated for the total scale and each dimension. Reliability indices will include Cronbach's alpha and McDonald's omega. In general, alpha and omega values of 0.70 or higher will be considered acceptable, and values of 0.80 or higher will indicate good internal consistency.

During final scale formation, changes in internal consistency after deleting individual items, item-total correlations, and factor loadings will also be examined. However, item retention will not be determined solely on the basis of any single statistical index; instead, decisions will be made by integrating theoretical necessity, content representativeness, and the overall stability of the scale structure.

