6.5.4 Criterion-Related Validity

If external variables theoretically related to excessive emotional behavior are measured in the study, criterion-related validity will be further examined through correlation analyses. For example, correlations may be examined between the Excessive Emotional Behavior Scale and constructs such as anxiety, depression, perceived stress, experiential avoidance, difficulties in emotion regulation, mindfulness, or resilience. Theoretically, the total score and relevant dimension scores of the Excessive Emotional Behavior Scale are expected to be positively correlated with anxiety, depression, stress, and experiential avoidance, and may be negatively correlated with mindfulness, cognitive flexibility, or resilience. Findings consistent with these expectations will provide further support for the validity of the scale.

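### The alpha/omega cut-offs in 6.5.1 can pass a total score that reflects little common construct, and the models bearing on this are only conditionally planned

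*Combined protocol and SAP*

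**What the plan says.** Hypothesis 1 (2.3) describes a construct with four dimensions. Section 6.5.1 then states that "internal consistency will be evaluated for the total scale and each dimension". "Reliability indices will include Cronbach's alpha and McDonald's omega", and "alpha and omega values of 0.70 or higher will be considered acceptable, and values of 0.80 or higher will indicate good internal consistency". The same cut-offs serve the total and the dimensions. The text does not say which omega is meant or from which model it is computed.

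The total is put to use. Section 6.3.1 screens items against it, and 6.5.4 expects "the total score and relevant dimension scores" to correlate with anxiety, depression and related constructs.

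The plan is not consistent on the models that bear on a total score:
- 6.4.1 makes evaluating alternative structural models part of the main purpose of Stage 2, and 6.8 lists the comparison among the results to be reported. Neither attaches a condition.
- 6.4.2 makes the comparison conditional: "If theoretically warranted, several competing models may also be compared, such as a one-factor model, a correlated four-factor model, and a higher-order factor model". Section 6.1 adds a second condition, that the Stage 2 sample is large enough.

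Section 6.4.2 also takes as its first model "the four-factor structure identified in the exploratory factor analysis", while 6.3.4 provides for what happens "if the empirical results deviate from the theoretical expectations".

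**The concern.** Alpha and omega-total measure how much of a sum score's variance is not item-specific error. Neither shows that the sum reflects one construct. With four clusters of well-correlated items, the within-cluster covariance can carry alpha past 0.70 or 0.80 even when the clusters have little or nothing in common.

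No other rule in the plan covers this. Section 6.5.3 uses correlations among dimensions only as an upper bound, so low correlations count in the scale's favour. No lower bound, general-factor index or condition for using a total is given.

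The scale is the study's product. A total labelled good is likely to be read by later users as one quantity, and its correlations in 6.5.4 would be interpreted that way.

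**Working it through.** The plan derives no reliability figure, so there is none to reproduce; 0.70 and 0.80 are decision thresholds.

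**Inputs from the document.** 40 initial items and four dimensions (opening of Section 6); at least three items per dimension, so at least 12 with four dimensions (6.6); minimum primary loading 0.45 (6.3.5); AVE target 0.50 (6.5.2), which under equal loadings implies √0.50 = 0.707, taken as 0.71; item-total screen 0.35 (6.3.1).

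**Assumptions.** Standardised items, m items in each of four dimensions, equal loadings λ, one common inter-factor correlation φ, and no cross-loadings. Section 6.3.3 expects correlated dimensions but gives no value, so φ is varied from 0 to 0.7.

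**Formulas**, with p = 4m items:
- Variance of the total: V = p + 4m(m−1)λ² + (p² − 4m²)λ²φ
- alpha = [p/(p−1)] × (1 − p/V)
- omega-total = 1 − p(1−λ²)/V
- omega-hierarchical = p²λ²φ/V, because each item loads λ√φ on the general factor implied by equal correlations

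**Worked case: 24 items, λ = 0.71, φ = 0.1.** λ² = 0.5041.
- V = 24 + 120 × 0.5041 + 432 × 0.5041 × 0.1 = 24 + 60.49 + 21.78 = 106.27
- alpha = (24/23)(1 − 24/106.27) = 0.81
- omega-total = 1 − 24 × 0.4959/106.27 = 0.89
- omega-hierarchical = 576 × 0.5041 × 0.1/106.27 = 0.27

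| Items | λ | φ | V | alpha | omega-total | omega-hierarchical |
|---|---|---|---|---|---|---|
| 20 | 0.71 | 0 | 60.33 | 0.70 | 0.84 | 0 |
| 24 | 0.71 | 0.1 | 106.27 | 0.81 | 0.89 | 0.27 |
| 40 | 0.71 | 0 | 221.48 | 0.84 | 0.91 | 0 |
| 40 | 0.60 | 0.1 | 212.80 | 0.83 | 0.88 | 0.27 |
| 12 | 0.71 | 0 | 24.10 | 0.55 | 0.75 | 0 |
| 24 | 0.60 | 0 | 67.20 | 0.67 | 0.77 | 0 |
| 40 | 0.45 | 0 | 112.90 | 0.66 | 0.72 | 0 |
| 24 | 0.60 | 0.5 | 144.96 | 0.87 | 0.89 | 0.72 |
| 24 | 0.60 | 0.7 | 176.06 | 0.90 | 0.91 | 0.82 |
| 40 | 0.60 | 0.5 | 385.60 | 0.92 | 0.93 | 0.75 |
| 40 | 0.60 | 0.7 | 472.00 | 0.94 | 0.95 | 0.85 |

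The first four rows pass on both coefficients with little or no common construct. In the next three, alpha falls below 0.70 but omega-total does not, so the outcome turns on which coefficient is meant and whether both must pass. In the last four the total is well supported.

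**Does the Stage 1 screen prevent this?** The correlation of an item with the total that contains it is, at φ = 0, [1 + (m−1)λ²]/√V. With λ = 0.71 this is 5.537/14.882 = 0.372 for 40 items and 3.016/7.767 = 0.388 for 20 items. Both clear 0.35 with unrelated dimensions.

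**Would higher-order fit alone detect it?** No. If all four factors correlate at 0.10, a higher-order model with second-order loadings √0.10 = 0.316 reproduces every correlation exactly, while omega-hierarchical stays at about 0.27 in the two φ = 0.1 rows above.

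**The case against.** The strongest reply is that 6.5.1 claims internal consistency, not a single construct, and that omega-total is a legitimate reliability for a multidimensional composite. That is correct as far as it goes. It does not answer what 6.5.4 does next, which is to relate the total to external criteria with no condition on what the total represents.

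Three stronger readings are tempting, and the documents do not support them.

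- **That item count alone carries nearly any set of 20 to 40 items past the cut-off.** Alpha also depends on loadings and correlations. With uncorrelated dimensions it is 0.66 for 40 items at the plan's minimum loading of 0.45, and 0.67 for 24 items at 0.60.
- **That Hypothesis 1 would be accepted on four-factor fit alone.** Section 6.3.4 uses parallel analysis to set the number of factors, and 6.5.3 compares the square root of AVE with the inter-dimension correlations. If one factor held, those correlations would be near 1 and the AVE comparison would fail. These checks bear on whether separate dimensions are needed. They do not bear on whether a total is justified.
- **That the plan ignores competing models.** Sections 6.4.1 and 6.8 intend them. The defect is that 6.1 and 6.4.2 make them conditional.

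It is also fair to say that the dimensions may turn out to be well correlated, as 6.3.3 expects, in which case the total is defensible. The four-factor model will display those correlations, but no rule in the plan uses them to decide.

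**Conclusion.** The concern holds as a gap in the decision rule, not as a prediction that the total will be poor. Applied as written, 6.5.1 can label a total good when omega-hierarchical is 0.27 (24 items, loading 0.71, correlation 0.1) or 0 (40 items, loading 0.71, correlation 0). It can equally pass a total with omega-hierarchical of 0.72 to 0.85, and the rule cannot tell these cases apart. The figures are population values under equal loadings and a common inter-factor correlation; the risk depends on final length, loadings and correlations, none of which the documents fix.

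Two wording defects add to it. The status of the competing models differs between 6.4.1 and 6.8 on one side and 6.1 and 6.4.2 on the other. And 6.4.2 presupposes a four-factor exploratory result that 6.3.4 does not guarantee, so the first Stage 2 model is undefined if Stage 1 retains another number.

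**What to change.** **6.5.1 and 6.5.4.** Keep alpha and omega with their cut-offs for each dimension. For the total, name the coefficients and report omega-hierarchical beside omega-total. Interpret the total as one construct in 6.5.4 only if omega-hierarchical meets a criterion written into the SAP before Stage 2 data are seen. Treat higher-order fit as supporting evidence only. If the criterion is not met, dimension scores are primary.

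**6.1 and 6.4.2.** Bring these into line with 6.4.1 and 6.8, so that four models are always fitted in Stage 2: the structure retained in Stage 1 whatever its number of factors, the theorised four-factor model, the one-factor model and the higher-order model. State in advance the margin for concluding that one factor fits worse, for example a difference in CFI. A margin is needed because the one-factor model is nested in the correlated four-factor model and can never have the smaller chi-square.

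**Cost.** SAP wording and a few extra model fits on the same data, with no new participants or measures. The total-score figure may look less favourable than alpha would.

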6.5.2 Convergent Validity

Convergent validity will be assessed using composite reliability (CR) and average variance extracted (AVE). In general, CR values of 0.70 or above and AVE values of 0.50 or above will be considered indicative of satisfactory convergent validity. If the AVE of an individual dimension is slightly below the recommended threshold but CR is adequate and the item content has clear theoretical value, the results will be interpreted in light of the overall structure and relevant literature.

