6.6 Principles for Final Item Selection

The final number of items in the formal scale will not be fixed in advance but will be determined after completion of item analysis, exploratory factor analysis, confirmatory factor analysis, and reliability and validity testing. Final item retention will follow the following principles: first, items should show satisfactory statistical performance, including adequate factor loadings, reasonable communalities, and a positive contribution to internal consistency; second, item content should accurately reflect the core meaning of the intended dimension; third, each dimension should retain a sufficient number of items to ensure structural stability and content representativeness. In principle, each dimension should retain no fewer than three items to ensure the basic stability of latent variable measurement.

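### If a residual correlation between two items of one dimension is kept in the Stage 2 model, alpha, and omega or CR computed without that covariance, overstate reliability under that model, mainly for three- or four-item dimensions

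*Combined protocol and SAP*

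**What the plan says.** Four sections of the combined protocol and SAP bear on this point.

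- **6.4.5 (model modification).** If initial fit is unsatisfactory, limited and theoretically justified changes may be made, "such as residual correlations arising from semantically similar items" being one example.
- **6.5.1 (internal consistency).** Once the structure is settled, "internal consistency will be evaluated for the total scale and each dimension". On the choice of coefficients the section says: "Reliability indices will include Cronbach's alpha and McDonald's omega". The standard it then sets is: "In general, alpha and omega values of 0.70 or higher will be considered acceptable, and values of 0.80 or higher will indicate good internal consistency". The same section looks at the change in internal consistency when single items are dropped.
- **6.5.2 (convergent validity).** "CR values of 0.70 or above and AVE values of 0.50 or above will be considered indicative of satisfactory convergent validity". There is some latitude, with the condition worded as: "If the AVE of an individual dimension is slightly below the recommended threshold but CR is adequate". Provided that what the items cover also matters on theoretical grounds, such a finding is then read in context.
- **6.6 (final item selection).** Retained items should make "a positive contribution to internal consistency", and a dimension may be as short as three items.

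None of these sections gives a formula for omega or CR. None says whether a retained residual covariance enters the variance of the total score.

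**The concern.** Freeing a residual correlation moves part of the covariance between two items out of the dimension's factor. Alpha cannot follow that decision, because it treats all inter-item covariance as reliable variance. The usual CR formula errs in the same direction by a different route: the residual covariance is not in its numerator, but it is also left out of the denominator, so total variance is understated. Omega computed in that form has the same fault, and omega from a one-factor fit that ignores the residual correlation is inflated much as alpha is.

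The reliability reported for a dimension could then disagree with the model it is reported under, always upward when the residual correlation is positive. Good internal consistency is one of the hypotheses in 2.3. The official title promises long and short forms, so short dimensions are a realistic outcome. Alpha-if-deleted carries the same bias into item selection.

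**Working it through.** **Inputs from the documents.** Cut-offs of 0.70 and 0.80 for alpha and omega (6.5.1); 0.70 for CR and 0.50 for AVE (6.5.2); a minimum of three items per dimension (6.6). The plan states no expected reliability, so there is no figure of its own to reproduce.

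**Assumptions.** k standardised items with equal loading L, one item pair with residual correlation r, and CR in its usual form. The documents give no values for L or r, so a range is shown.

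**Formulas.** With error variance t = 1 − L²:

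- total-score variance V = (kL)² + kt + 2rt
- model-consistent omega = (kL)² / V
- usual CR = (kL)² / [(kL)² + kt]
- alpha = [k/(k − 1)] × (1 − k/V)
- AVE = L²

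**Worked case: k = 3, L = 0.67, r = 0.4.** t = 1 − 0.4489 = 0.5511; (kL)² = 2.01² = 4.040; kt = 1.653; 2rt = 0.441; V = 6.134.

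- omega = 4.040/6.134 = 0.659
- CR = 4.040/5.693 = 0.710
- alpha = 1.5 × (1 − 3/6.134) = 0.766

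With r = 0, all three equal 0.710.

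**Other cases.**

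| k | L | r | alpha | usual CR | model-consistent omega | AVE |
|---|---|---|---|---|---|---|
| 3 | 0.67 | 0.3 | 0.753 | 0.710 | 0.671 | 0.449 |
| 3 | 0.65 | 0.3 | 0.735 | 0.687 | 0.647 | 0.423 |
| 3 | 0.60 | 0.4 | 0.707 | 0.628 | 0.571 | 0.360 |
| 4 | 0.61 | 0.4 | 0.739 | 0.703 | 0.664 | 0.372 |
| 6 | 0.66 | 0.4 | 0.831 | 0.822 | 0.803 | 0.436 |
| 10 | 0.60 | 0.3 | 0.851 | 0.849 | 0.841 | 0.360 |

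In the three- and four-item rows, alpha exceeds omega by 0.075 (four items) to 0.135 (three items, L = 0.60), and CR exceeds it by about 0.04 to 0.06. For k = 3, L = 0.65, r = 0.3, omega from a one-factor fit that ignores the residual correlation is 0.743 against 0.647.

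**How much residual correlation is needed.** For three items with alpha exactly 0.70, model-consistent omega is 0.653 at r = 0.15. With CR exactly 0.70, it takes r = 0.40 to bring omega down to 0.648.

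**Sampling.** With an assumed 275 Stage 2 participants (half of the 550 in 5.1), k = 3, L = 0.66 and r = 0.4, sample alpha reached 0.70 in about 98% of 4,000 multivariate normal samples. The population values there are alpha 0.758, CR 0.698, omega 0.646 and AVE 0.436.

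**Item deletion.** Take four items at L = 0.67 with one pair at r = 0.4. Dropping an item outside the pair leaves the worked case above: alpha 0.766, omega 0.659. Dropping one of the pair leaves three items with r = 0: alpha and omega both 0.710. Alpha therefore favours keeping the pair, and omega favours breaking it up.

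**The case against.** The strongest reply is that the plan does not rest on alpha. Section 6.5.1 names the two coefficients together, and the natural reading is that both should reach the cut-off. Reliability is assessed after the structure is settled, which suggests omega from the final model. That omega is 0.57 to 0.67 in every three- and four-item case above, so the dimension would be flagged. AVE is a second check: it is 0.36 to 0.45 in those cases. At AVE exactly 0.50, three items with one pair give omega = 4.5/(6 + r), which stays at or above 0.70 up to r of about 0.43.

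This much stands. A reader might infer that a dimension with reliability near 0.65 would pass the plan, and might take the 98% as the chance of that. The documents do not support either reading. The 98% concerns alpha alone, at an assumed n and with normal items; population CR, omega and AVE all miss their cut-offs in that case. CR is in any event a convergent-validity check here, not a reliability criterion.

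The chain of conditions is also long: unsatisfactory initial fit, a justified modification, a pair within one dimension, and few items from a pool of 40. Stage 1 may already delete redundant items (6.3.5), and no single index decides retention (6.5.1). Finally, covariance from similar meaning may be stable, specific content and not error, so omega here means the share of score variance due to the modelled factor.

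The upward bias remains. The plan does not say which omega it will use, and the software default for CR may omit the residual term. AVE is only a partial check: a slight shortfall can be excused by an adequate CR, and in the worked case that CR is 0.71 without the residual covariance and 0.66 with it.

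**Conclusion.** The point holds as a conditional one. When a positive residual correlation within a dimension is retained, alpha as prescribed overstates reliability under the accepted model. Omega and CR do so too if the residual covariance is left out of the denominator. Under equal assumed loadings, the excess in alpha for three- and four-item dimensions is about 0.08 to 0.14 at r of 0.3 to 0.4. It is about 0.03 for six items at r = 0.4, about 0.01 for ten items at r = 0.3, and zero when no residual correlation is added. It is not shown that a weak dimension would clear all the plan's criteria, since omega from the final model and AVE would usually flag it. The sizes rest on loadings and residual correlations that the documents do not give. The correction is worth making before Stage 2 data are seen, so that the choice of coefficient is not made afterwards.

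**What to change.** Three changes of wording are enough.

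1. **6.5.1 and 6.5.2:** state that omega and CR are computed from the final CFA, with every retained residual covariance included in the total-score variance (the denominator).
2. **6.5.1:** for any dimension with a retained residual correlation, compare this omega with 0.70 and 0.80, and report alpha descriptively.
3. **6.5.1 and 6.6:** for items in such a dimension, judge the contribution to internal consistency by the change in this omega, not by alpha-if-deleted.

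The cost is a few sentences and one extra term taken from CFA output that will exist anyway; no further data are needed. The downside is that some reported reliabilities become slightly lower.
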